8. STUDY PARTICIPANTS

8.1 Study Setting

80 patients with rectal cancer with an elective indication for surgery will be recruited from Queen Alexandra Hospital in Portsmouth during an estimated 2-year period. This study will be observational, and all data will be collected prospectively.

The reason for choosing an observational study is that there is very little evidence on the subject. To run a randomised controlled trial at this moment, without evidence that there might be a trend towards a significant difference, would be a very costly decision with a possibly unjustified burden to the patients.

Since the unit performs over 100 rectal resections a year amongst 3 surgeons and there is an approximately equal split between robotic and laparoscopic cases, randomisation for creating equal groups will not be necessary in this stage.

If this observational study proves to be of significant value, we will proceed with a larger, multicentre randomised trial, taking these results into account in the designing stages.

8.2 Overall Description of Study Participants

Patients with rectal cancer, up to 15 cm from the anal verge, with an indication for elective minimally invasive rectal cancer surgery.

8.3 Eligibility Criteria

Patient Inclusion Criteria

- Age 18 years or above.
- Diagnosed with rectal cancer, up to 15cm from the anal verge.
- Local MDT recommends rectal cancer surgery (i.e. (high) anterior resection, partial TME, complete TME)
- Patient assessed as fit for surgery (ASA I-III).
- Patient willing and able to give informed consent for participation in the study.
- Elective surgery.

Patient Exclusion Criteria

- Patient planned for Abdominoperineal Excision of Rectum (APER) or Hartmann's procedure
- Patients with confirmed or suspected metastatic disease.
- Pregnant or breastfeeding patients.
- Inflammatory bowel disease (IBD).
- Other known auto-immune disease which might influence the immune response (such as advanced liver disease, human immunodeficiency virus infection, Hepatitis B or C virus).
- Use of anti-inflammatory medication (i.e. corticosteroids, anti-inflammatory drugs, immune modulating drugs, chronic use of antibiotics (the use of NSAIDS and steroid asthma inhalers will not be considered an exclusion criteria).
- High pre-operative C-reactive protein (CRP) levels (>20).

9. SAMPLING

In our retrospective study we demonstrated IPSS and IIEF score differences of more than 5.0 points between the 2 groups (see preliminary data). Assuming a 3.75 IPSS score and 4.4 IIEF score difference and a 0.05 (two-sided) significance level, 35 patients will be required in each group to provide 80% power.

We also carried out simulated cumulative scores from the study-specific CRF based on the Likert-scale for independent validation of our initial analysis. Considering 80% power and a 0.05 (two-sided) significance level, a minimum of 36 patients were needed in each arm to demonstrate a minimum difference in the cumulative score of 1 between the groups. This sample size calculation was carried out using the "stats" module in R (ver. 3.4.2) using a two-sided independent means test.

We have considered a maximum of 10% loss to follow-up for the long-term functional outcomes in our population during sample size calculations and will thus seek to recruit a minimum of 80 patients into our study.

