7.2 Primary and Secondary Endpoints/Outcome Measures

Primary endpoints:

- 1. Assessment of functional outcomes by using validated questionnaires for bladder, bowel and sexual function pre-operatively, and after 3, 6 and 12 months.
 - International Prostatic Symptoms Score (IPSS) (male)
 - International Index of Erectile Function (IIEF) (male)
 - Female Sexual Function Index (FSFI) (female)
 - Kings Health questionnaire (female)
 - LARS-score (male/female) Not applicable at 3 and/or 6 months if the patient still has a stoma in situ at those respective follow-up moments
 - Vaizey score (male/female)
- 2. Measurement of stress response by taking blood samples at baseline and postoperative days 1, 3 and 5. Blood samples can be collected by anyone trained to do so and will be processed by an appropriately delegated member of the clinical team (including the research team). The following blood tests will be collected:
- White blood cell count (WBC)
- C-reactive protein (CRP)
- NLR (neutrophil lymphocyte ratio)
- IL-6
- IL-10
- TNFa
- MPO (neutrophil myeloperoxidase)

Some of the above blood tests (WBC, CRP, NLR, etc.) may be carried out as part of routine post-operative care. If these results are available, they can be used and additional sampling may not be required. Should these test results also be available for postoperative days 2 and 4, they can also be collected for use in this study, but this will be optional and no additional sampling will be done on these days.

Secondary outcomes:

- 1. Quality of life assessment using validated questionnaires (EORTC QLQ-C30/ CR29 and EQ-5D) at baseline, and after 3, 6 and 12 months.
- 2. Surgical outcomes, such as operative time, blood loss, stoma application, conversion, and intra-operative complications
- 3. Patient related outcomes:
 - a. Length of hospital stay
 - b. Opioid requirements and compliance with ERP
 - c. Worst vital signs post op
 - d. Worst pain scores
 - e. Time to flatus (in days) and return of bowel function
 - f. Early morbidity (up to 30-day postoperative complications, Clavien-Dindo Classification*)
 - g. Early mortality
 - h. Adverse events.
- 4. Optional: assessment of anorectal physiology after laparoscopic or robotic surgery in rectal cancer patients by using an anorectal manometry at baseline and after 1 year

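### Section 9 claims 80% power for IPSS and IIEF from a count of all patients, but only men complete those questionnaires, so the claim fails unless nearly all recruits are men

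*Protocol*

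**What the plan says.** Section 9 (Sampling) bases its first calculation on the two male urogenital scores: "Assuming a 3.75 IPSS score and 4.4 IIEF score difference and a 0.05 (two-sided) significance level, 35 patients will be required in each group". The power claimed for this number is 80%. No standard deviation is given. A second calculation, on a cumulative score simulated from the case report form, finds that "a minimum of 36 patients were needed in each arm to demonstrate a minimum difference in the cumulative score of 1 between the groups". After a maximum of 10% loss to follow-up, the investigators "will thus seek to recruit a minimum of 80 patients into our study".

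Section 7.2 lists the functional instruments with the sex each applies to: "International Prostatic Symptoms Score (IPSS) (male" and "International Index of Erectile Function (IIEF) (male". Women are given the FSFI and the Kings Health questionnaire instead. LARS and Vaizey are for both sexes. The synopsis repeats these labels.

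Section 8.3 admits anyone aged 18 or over who meets the clinical criteria, with no restriction or quota by sex. It excludes pregnant and breastfeeding patients, so women are clearly expected. Section 8.1 describes a roughly even division between robotic and laparoscopic cases. Section 13.2 names Student's t test for the comparison between groups.

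**The concern.** The calculation counts patients, but only men can supply the scores on which it rests. Women add to the 80 and contribute nothing to the IPSS or IIEF comparison. Nothing in section 9 allows for this, because the only inflation is for loss to follow-up.

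What is at stake is how the IPSS and IIEF results are read. A non-significant difference would be credited with a 20% risk of having missed the assumed effect, when the real risk is higher by an amount that depends on how many recruits are men. Section 8.1 says the study's results will inform the design of a randomised trial, so the power attached to each comparison should be right.

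**Working it through.** **Inputs from the protocol.** Two-sided alpha 0.05, power 80%, 35 per group, differences of 3.75 (IPSS) and 4.4 (IIEF), loss 10%, total 80 (all section 9); approximately even split (section 8.1); t test (section 13.2); IPSS and IIEF for men only (section 7.2).

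**Inputs not in the protocol.** The male share, taken here as 50-70%. The standard deviations, back-solved on the assumption that each instrument needs exactly 35 per group.

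**Step 1: the total.** 36 / 0.9 = 40 per arm, or 80 in all, which is the stated total. 35 / 0.9 = 38.9, rounded up to 39 per arm, or 78. So the total of 80 corresponds to the 36 per arm of the second calculation. After 10% loss, 80 × 0.9 = 72 patients remain, 36 per arm.

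**Step 2: the plan's own figure.** With no standard deviation stated, the 35 cannot be reproduced independently; only the standardised difference d that it implies can be found.
- Normal approximation: d = (1.960 + 0.842) × √(2/35) = 0.670.
- Noncentral t, with 68 degrees of freedom and noncentrality d × √(35/2), solved for 80% power: d = 0.679.

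With d = 0.679, the implied standard deviations are 3.75 / 0.679 = 5.52 (IPSS) and 4.4 / 0.679 = 6.48 (IIEF). These return 35 per group by construction.

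**Step 3: how many men the claim needs.** 35 evaluable men out of 36 evaluable patients per arm is 35 / 36 = 97%. With no loss at all it is 35 / 40 = 87.5%.

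**Step 4: power at a given male share m.** Evaluable men per arm are 36 × m with 10% loss and 40 × m with none. Power comes from the noncentral t with d = 0.679, n men per arm, 2n − 2 degrees of freedom and noncentrality d × √(n/2).

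| Male share (assumed) | Men per arm, 10% loss | Power | Men per arm, no loss | Power |
|---|---|---|---|---|
| 50% | 18.0 | 50.8% | 20 | 55.3% |
| 60% | 21.6 | 58.7% | 24 | 63.5% |
| 70% | 25.2 | 65.7% | 28 | 70.4% |
| 80% | 28.8 | 71.7% | 32 | 76.3% |
| 100% | 36.0 | 81.1% | 40 | 85.1% |

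The normal approximation, with its own d of 0.670, gives 52.0%, 59.5% and 66.2% for the first three rows with loss.

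**Step 5: difference detectable with 80% power, 10% loss.** The required d is 0.961, 0.873 and 0.805 at 50, 60 and 70% men. Multiplying by the implied standard deviations:
- IPSS: 0.961 × 5.52 = 5.3; 0.873 × 5.52 = 4.8; 0.805 × 5.52 = 4.4 points, against the 3.75 planned.
- IIEF: 0.961 × 6.48 = 6.2; 0.873 × 6.48 = 5.7; 0.805 × 6.48 = 5.2 points, against the 4.4 planned.

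**The case against.** Several points can fairly be made for the plan.

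**The percentages are not the protocol's.** A reader might take 51-66% as the study's power. The documents do not support that: the male share is assumed, the loss is stated as a maximum and the 80 as a minimum, and one d is imposed on both instruments. If only one instrument drove the 35, the other had a larger standardised difference and loses less. This stands as a limit on the size of the shortfall. It does not remove the shortfall, because the 97% in step 3 needs no assumed male share.

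**Section 9 states 80% power twice.** A reader might infer that the study's whole power basis collapses. It does not follow: the cumulative-score calculation carries no restriction by sex and may apply to all 80. The data collection forms are not reproduced, so its content cannot be judged. But no such score appears among the endpoints in section 7.2 or in the analysis in section 13.2, and a calculation on a different quantity cannot validate the one for IPSS and IIEF.

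**The planned differences are cautious.** Section 9 reports retrospective differences above 5.0 points on both scores. With the implied standard deviations and 60% men, power for 5.0 points is about 83% for IPSS and 70% for IIEF. That is a fair mitigating point, but the 80% is claimed for 3.75 and 4.4.

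**The study is observational with many primary measures.** LARS, Vaizey and the blood markers are collected in both sexes and are untouched by this point. A reader might also infer that a null IPSS or IIEF result would block the randomised trial. Section 8.1 ties that trial to the study proving of significant value, and makes neither score a gate.

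**Conclusion.** The point holds for the power statement on IPSS and IIEF. Section 9 applies a requirement for men to a cohort of both sexes, and the 80% it claims for these two scores is not met unless about 97% of recruits are men at the planned loss, or 87.5% with none.

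Under the stated assumptions (50-70% men, even split, d of about 0.68 for each instrument), power is about 51-66% with 10% loss and 55-70% without. At 10% loss, the risk of missing the assumed difference is then about 34-49% rather than 20%, and the detectable differences are about 4.4-5.3 IPSS points and 5.2-6.2 IIEF points.

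The fault is a mismatch between the endpoint and the population counted. The loss adjustment itself is correct, since 36 per arm does become 80 in total. The finding does not show that 80 is the wrong number to recruit.

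**What to change.** Restate section 9 for IPSS and IIEF as comparisons among men. Give the standard deviation used for each score and its source, the expected share of men in the unit's eligible patients, the resulting number of evaluable men per arm after loss, and the power at 3.75 and 4.4 points or the difference detectable with 80% power. These should be the sponsor's own figures; the ranges above only show the likely scale.

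For the cumulative score, either define it and tie it to a listed endpoint that both sexes complete, or stop citing it as validation of the IPSS and IIEF calculation.

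The change is to wording only. Enrolment, procedures and data collection stay as they are. The cost is a less favourable stated power for these two scores.

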13.2 Analysis of Endpoints

We will analyse summary statistics for each allocation group, including means and standard deviations for normally distributed data and medians and interquartile ranges for non-normally distributed data.

Student's t test will be used to analyse the differences between the two groups (L-TME vs. R-TME). The paired t test will be used to compare postoperative urogenital, bowel and sexual functions in both groups to the preoperative functions. Fisher's exact test will be used for categorical data (e.g., age, sex, tumour location, T and N stage, and radiation therapy). A P-value of 0.05 will be considered statistically significant.

The analysis of the differences between groups of blood cell counts or number of lymphocyte subsets, and clinic pathological variables will be performed using Chi-square tests, Kruskal–Wallis tests, and analysis of variance tests. A P-value of 0.05 will be considered statistically significant.

Analysis of the QLQ-C30 and QLQ-CR29 questionnaires will be performed in accordance with the EORTC guidelines. Time to definitive deterioration in quality of life, with the use of a 10-point minimal clinically important difference, will be analyzed with the use of the Kaplan–Meier method and the log-rank test. Descriptions (by visit) and graphs will be presented.

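### The 36-per-arm calculation in Protocol section 9 rests on a simulated cumulative score that is not a listed endpoint, so it cannot confirm the IPSS/IIEF power calculation

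*Protocol*

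**What the plan says.** Section 9 of the Protocol first works from the team's retrospective study: "Assuming a 3.75 IPSS score and 4.4 IIEF score difference and a 0.05 (two-sided) significance level, 35 patients will be required in each group", at 80% power. No SD is printed.

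It then reports a second exercise, described as "simulated cumulative scores from the study-specific CRF based on the Likert-scale for independent validation of our initial analysis". The settings are given as "Considering 80% power and a 0.05 (two-sided) significance level", the method as "using a two-sided independent means test", and the result is that "a minimum of 36 patients were needed in each arm to demonstrate a minimum difference in the cumulative score of 1 between the groups". The items, range, time point and SD of this score are not given.

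The section closes with an allowance of at most 10% for loss to follow-up and a recruitment minimum of 80. It does not say which of the two figures was inflated.

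Section 7.2 defines the first primary endpoint as "Assessment of functional outcomes by using validated questionnaires for bladder, bowel and sexual function pre-operatively, and after 3, 6 and 12 months". It names six instruments: IPSS and IIEF for men, FSFI and King's Health for women, and LARS and Vaizey for both sexes. LARS does not apply at 3 or 6 months while a stoma is in place. The second primary endpoint is seven blood markers. The synopsis and section 10.2 list the same instruments and markers. Section 13.2 compares the two groups by Student's t test and names no cumulative score.

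**The concern.** A sample-size calculation supports a study only if its outcome is one that the study will analyse. In the protocol text the cumulative Likert score occurs in section 9 and nowhere else, yet the figure derived from it reproduces the recruitment target exactly and is presented as a check on the IPSS/IIEF figure.

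A reader of section 9 sees two calculations that agree closely, one said to validate the other, and will have more confidence in 80% power for function than the text justifies. The first calculation needs real support: it prints no SD, and it treats two questionnaires for men as if all patients in each group would complete them. A second calculation on a different and undefined score supplies neither the SD nor the number of men. At stake is how a non-significant functional result would be read, since it could be taken as coming from a study whose 80% power had been confirmed twice.

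**Working it through.** **Inputs.** From section 9: two-sided 0.05; 80% power; 35 per group for differences of 3.75 (IPSS) and 4.4 (IIEF); 36 per arm for a difference of 1 in the cumulative score; 10% loss; at least 80 recruits. From section 8.1: roughly equal groups. From section 7.2: IPSS and IIEF are for men only. The proportion of men is not given, so 50% to 70% is an assumption.

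**1. Recruitment target.** Recruits per arm = n / (1 − 0.10), rounded up.

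| Evaluable per arm | Per arm after 10% loss | Total |
|---|---|---|
| 35 | 35 / 0.9 = 38.9, so 39 | 78 |
| 36 | 36 / 0.9 = 40 | 80 |

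Inflating by 1.1 gives the same rounded figures per arm (38.5, so 39; 39.6, so 40). Exactly 80 therefore follows from 36. The two calculations differ by two recruits.

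**2. What 36 per arm implies.** No SD is stated, so the 36 cannot be reproduced; only the implied SD can be solved. For a two-sample t test at two-sided 0.05 and 80% power, n = 36 per arm detects a standardised difference d = 0.670. Implied SD = difference / d = 1 / 0.670 = 1.49. The normal approximation gives d = 0.660 and SD = 1.51.

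**3. What 35 per group implies.** By the same test, n = 35 gives d = 0.679.
- IPSS: 3.75 / 0.679 = 5.52.
- IIEF: 4.4 / 0.679 = 6.48.

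The two calculations concern different scores with different implied spreads (1.49 against 5.5 and 6.5). Their sample sizes agree because the standardised differences nearly coincide (0.670 and 0.679). That coincidence is not evidence that the IPSS and IIEF differences or SDs are right.

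**4. What the planned size delivers for listed endpoints.** Take 36 evaluable patients per arm and d = 0.679, the effect implied by section 9 for IPSS and IIEF.

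| Assumed share completing the instrument | Evaluable per arm | Power at d = 0.679 | Difference detectable at 80% power |
|---|---|---|---|
| 100% | 36 | 81% | 0.67 SD |
| 70% | 0.70 × 36 = 25.2 | 66% | 0.81 SD |
| 50% | 0.50 × 36 = 18 | 51% | 0.96 SD |

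The first row reproduces the protocol's 80% for IPSS and IIEF, but only if every patient contributes these scores. The other rows show the range for an instrument restricted to men.

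**The case against.** The strongest reply is that the study's power claim does not depend on the cumulative score. The first calculation ties 80% power at 35 per group to IPSS and IIEF, both listed primary endpoints, and 80 recruits cover the 78 it needs. Section 9 never says that 36 was the figure inflated, and 78 could simply have been rounded up. Removing the second calculation changes no design quantity. All of this stands, and it limits the point to the second calculation.

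A reader might infer that no power statement in section 9 attaches to any endpoint. The first calculation rules that out.

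A reader might also infer that the score was invented or exists nowhere in the study. The documents do not support this. Section 9 says that it comes from the study's own CRF, the data collection forms in Appendix 7 are present only as a heading, and a statistical analysis plan may exist. The supportable statement is that the protocol text neither defines the score, lists it as an endpoint nor analyses it. A definition on a form would still not make it an endpoint of section 7.2. Nor does the protocol say what the simulation was based on, so nothing can be concluded about where its spread came from.

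Finally, a reader might work out the power for a 1-point difference on IPSS or IIEF, or for a cumulative-score SD above 1.49, and treat a low result as a defect. The protocol proposes neither. It plans for 3.75 and 4.4 points and prints no SD, so such figures show no error.

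**Conclusion.** The point holds for the second calculation only. The 80% power quoted with 36 per arm belongs to no endpoint that the protocol lists, and that calculation cannot act as independent validation of the IPSS/IIEF figure. No arithmetic slip is shown: 2 × 36 / 0.9 = 80 is correct.

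The effect on the recruitment target is two patients, 80 against 78. The larger effect is on how the power is read. Section 9's 80% for IPSS and IIEF holds only if all patients complete them; with men an assumed 50% to 70% of 36 evaluable per arm it is about 51% to 66%. These figures rest on equal groups, a two-sample t test, the standardised difference implied by 35 per group, the assumed share of men, and complete data from the men counted. The change is worth making because it corrects a stated basis for size and power through wording alone.

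**What to change.** In section 9 of the Protocol:

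- Keep 80 recruits.
- Remove the cumulative-score calculation, and the statement that it independently validates the first, as a basis for sample size and power.
- Print the SDs used with the differences of 3.75 and 4.4. The values implied by 35 per group are about 5.5 (IPSS) and 6.5 (IIEF); the actual SDs should come from the retrospective study.
- State that 36 evaluable per arm gives 80% power, two-sided 0.05, for a difference of 0.67 SD only on an instrument completed by all patients.
- For IPSS, IIEF, FSFI and King's Health, state power and detectable difference at the expected number of men or women per arm. With men at an assumed 50% to 70% of 36, IPSS/IIEF power is about 51% to 66%, and the difference detectable at 80% power is about 0.96 to 0.81 SD.
- Leave LARS and Vaizey in SD units. Section 5 says that the retrospective study did not assess bowel function, so it cannot supply SDs for them. For LARS at 3 and 6 months, patients with a stoma also reduce the number available.

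The cost is protocol wording, with no extra patients or data. The downside is that the stated power becomes less favourable and section 9 loses its apparent second confirmation.

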10. STUDY PROCEDURES

10.1 Recruitment and informed consent

The study will be offered prospectively to patients undergoing elective bowel resection for colorectal cancer or benign pathological cancer. Following the decision to operate, the clinical team will identify these patients as potential patients and introduce them to the study. The Participant Information Sheet (paper or digital) will be given to potential patients in person or remotely (via post or email).

Patients will be given sufficient time to consider their involvement and ask any questions they have. Potential patients will be clearly informed that involvement is completely voluntary, and they can decline or withdraw at any time without reason or penalty. We will retain the data we have already collected if they withdraw and will continue to collect information from their medical records unless they ask us not to.

The Prime Investigator has overall responsibility for informed consent at their site to ensure staff listed on the delegation log are appropriately trained, experienced and competent in receiving informed consent. Informed consent will be received by an appropriately trained member of the research team who has been delegated to do so and has been signed onto the delegation log for this task by the CI/PI.

In person informed consent

Patients will be provided with the study information as described above. Patients are able give informed consent once they feel they have had sufficient time to consider participation. No minimum timeframe is defined, as some patients may read the information and wish to consent at that time. After consent, patients will have the opportunity to further consider their involvement and withdraw by contacting the research team. Patients who wish to have more time to consent are able to do so and, when ready, can give informed consent remotely to prevent additional visit burden.

Remote consent

Remote consent can be received by witnessed verbal consent via telephone or by trust approved video call platforms. Patients will be provided (in person/ post / email) with a copy of the Participant Information Sheet (paper or digital) to read and review. The call/video must be witnessed by a member of staff at site who is not part of the study team (this may be a member of the clinical team or a research nurse from another team) who will confirm in writing that the study was explained, questions were answered, time was given for patients to consider and patients were informed that all involvement is voluntary and that they can withdraw at any time without penalty (this document should be signed and a copy filed in site file and patients medical notes). After remote verbal consent is received the member of the study team receiving consent will sign the consent form and clearly document the consent was performed via remote witnessed consent. The consent form is to be countersigned by the witness. The original consent form should be filed in the site file, a copy of the consent form provided to the patient (post or email) and another copy filed in the medical notes. There will be no active recruitment strategy (such as advertisements) other than selecting patients from the participating centres by the research team, see below.

Recruitment time frame

The unit performs over 100 rectal resections a year with 3 surgeons and there is approximately an equal split between robotic and laparoscopic cases. Therefore, we estimate 100 potentially eligible cases will take place each year. Allowing for exclusion criteria and patients declining participation, and assuming a recruitment rate of 60%, we estimate recruitment will be completed two years from study opening.

